### Cohort 2:

Procedural complications will be presented and tabulated according to MedDRA classification. Descriptions of procedural complications will include the start date, the stop date (if it resolved), the severity and seriousness of the procedural complication, and the outcome.

Reported procedural complications will be summarized by the number of subjects reporting the events, as well as by SOC, PT, severity, and seriousness. For the summary of procedural complications by severity, each subject will be counted only once within a SOC or a PT by using the procedural complications with the highest intensity within each category for each analysis.

All information pertaining to procedural complications noted during the trial will be listed by subject, detailing verbatim, SOC, PT, start date, stop date, intensity, and outcome. The procedural complication onset will also be shown relative (in number of days) to the Day 1 skin sample collection.

#### **9.3.4.2 Open-Label Extension Period**

Safety analyses will follow general considerations in previous Section [9.3.4.1](#) with the following exceptions:

- Summaries will be provided for 1) treatment group in the OLE and for 2) randomized treatment groups in vehicle-controlled treatment period.
- Change from baseline will be analyzed using change from vehicle-controlled treatment period baseline for subjects who received delgocitinib during the vehicle-controlled treatment period, and change from OLE baseline for subjects who received placebo during the vehicle-controlled treatment period.

Only descriptive statistics will be presented.

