Abbreviations: anti-HBc, antibody to hepatitis B core antigen; BID, twice daily; ET, early termination; FFA, frontal fibrosing alopecia; FFASS, Frontal Fibrosing Alopecia Severity Score; HBV, hepatitis B virus; HBsAg, hepatitis B surface antigen; HCV, hepatitis C virus; HIV, human immunodeficiency virus; IMP, investigational medicinal product; LPPAI, lichen planopilaris activity index; NRS, Numerical Rating Scale; OLE, open-label extension; TSH, thyroid-stimulating hormone; V, visit.

a For female subjects of childbearing potential, serum pregnancy test at screening and urine pregnancy test at other specified visits.

b Including height and weight. Height will be measured only at screening.

c The lesional target area should be treated with the IMP and should be approximately 3 cm x 6 cm (or equivalent). However, a smaller lesional target area can be selected if tape stripping is performed from the same area where trichoscopy/hair counts is performed or if sample is collected adjacent/close to the lesional target area (refer to Section 8.3.2 for details). If needed, two small lesional target areas (totalling approximately the same size) could be selected to allow for skin samples collection.

d Subjects will complete their NRS at home on a daily basis starting approximately 7 days prior to Day 1 and up to Day 8. On Day 1, the NRS will be completed at the site prior to the first IMP application. After Day 8, the NRS will be completed at the site at the specified visits only.

e Hair line measurements of lateral canthus (right and left) to hairline, lower glabellar crease to hair line, top of frontalis muscle to hair line, and mid brow to hair line (right and left).

f Medical photographs of the target area and the entire scalp (including the frontal hair line and right and left hair line areas).

g The morning application will be on site on visit days. Other IMP applications will be done at home. The first application of the OLE (delgocitinib cream 20 mg/g) is on the morning of Week 12, after all efficacy assessments and skin sample collections are completed. The last application of the OLE is the evening prior to the Week 24 visit. No IMP application will be done on the day of the Week 24 visit.

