## 2.2 Risk/Benefit Assessment

### 2.2.1 Known Potential Risks

A total of 15 clinical trials, 1 with oral delgocitinib (sponsored by JT), 11 with delgocitinib ointment (7 sponsored by JT and 4 sponsored by LEO Pharma A/S), and 3 with delgocitinib cream (sponsored by LEO Pharma A/S), have been completed and 2 clinical trials with delgocitinib cream are currently ongoing (sponsored by LEO Pharma A/S). In total, 54 subjects were dosed orally with delgocitinib (at doses between 1 and 100 mg) and 1635 subjects were exposed topically to delgocitinib ointment (1165 subjects at concentrations between 0.3 and 30 mg/g) or delgocitinib cream (470 subjects at concentrations between 1 and 20 mg/g).

Delgocitinib ointment and delgocitinib cream were well tolerated in the conducted clinical trials and systemic exposure to delgocitinib has been low. No clinical indication of any phototoxic potential was observed for delgocitinib cream when single occlusive application of delgocitinib was followed by light exposure in healthy subjects. Potential risks to humans that could arise from use of delgocitinib cream are local skin infection, and acneiform eruptions, which have been reported in clinical trials with delgocitinib ointment. Only few serious adverse events (SAEs) were reported in the completed clinical trials. Except for one, all SAEs were considered not related to treatment. There was no pattern in the reported preferred terms (PT). The one related SAE was an event of *Kaposi's varicelliform eruption* reported in a JT trial with delgocitinib ointment in Japanese subjects. The subject experiencing this event was hospitalized, and the event was resolved.

Generally, no clinically significant changes in laboratory test values, in systolic blood pressure, diastolic blood pressure, pulse rate, or body temperature were observed in subjects exposed to delgocitinib cream. Lymphocytopenia was observed in oral nonclinical toxicity studies and is considered a potential clinical consequence of systemic levels of delgocitinib. Lymphocytopenia is therefore considered an important potential risk for delgocitinib cream.

Further information related to nonclinical and clinical studies is available in the Investigator Brochure (IB).

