#### Cohort 1:

All subjects will read and sign an informed consent form (ICF) prior to any trial-related activities being performed. Subjects who fulfill all of the inclusion criteria and none of the exclusion criteria will be randomized into the trial. After a screening period of no more than 30 days (from Day -30 to Day -1), eligible subjects will be randomized (1:1) on Day 1 to apply delgocitinib cream 20 mg/g or vehicle cream BID for 12 weeks during the vehicle-controlled treatment period. All subjects who complete the vehicle-controlled treatment period will then continue into the OLE and apply delgocitinib cream 20 mg/g BID for 12 weeks. The OLE period will be followed by a 2-week safety follow-up period. For scheduled trial visits, subjects will come to the site on 9 occasions: screening, Day 1, Week 4, Week 8, Week 12, Week 16, Week 20, Week 24, and Week 26/early termination (ET).

On Day 1, a lesional target area on the scalp (eg, frontal, periauricular, or temporal area) that be treated with the IMP will be identified. To allow for the hair count/trichoscopy assessment and all samples collection (ie, skin biopsies, tape stripping, and skin swabs) the lesional target area should be approximately 3 cm x 6 cm (or equivalent). However, as tape strips can be collected from the same area where trichoscopy/hair counts is performed or can be collected adjacent/close to the lesional target area (refer to Section 8.3.2 for details), a smaller lesional target area may be acceptable. If needed, two small target areas (totalling approximately the same size) could also be selected to allow for skin samples collection and hair count/trichoscopy assessment. If two lesional target areas are selected, they should be of similar severity.

The following skin samples will be collected during the trial to assess molecular signature changes:

- Skin biopsies for transcriptomic and immunohistochemistry (IHC) analyses (n=3):
  - o *Day 1*: 2 skin biopsies (4-mm) will be collected prior to the first IMP application (1 from a lesional hair follicle within the target area and 1 from a non lesional hair follicle [eg, on the occipital scalp]).
  - o *Week 12*: 1 skin biopsy (4-mm) will be collected from a hair follicle within the lesional target area (outside the scar of previous biopsies).
- Skin swabs for microbiome analysis (n=3):

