## 6.3 Randomization

At the site, each screened subject will be assigned a subject identifier number during screening that will be used on all subject documentation. The subject identifier number will contain the site number (ie, 01) and the subject number and will be assigned in numerical order at the screening visit based on chronological order of screening dates (e.g., 01-010 for the 10th subject screened).

In Cohort 1, approximately 30 subjects will be randomized 1:1 to delgocitinib cream 20 mg/g or vehicle cream.

Further guidance and information about randomization assignment can be obtained in the study manual. The randomization number is to be recorded at the appropriate location in the source document and eCRF.

In Cohort 2, no randomization scheme will be used since no IMP will be applied.

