### 9.3.2 Baseline

Baseline will be defined separately for the vehicle-controlled treatment period and OLE as follows:

- Vehicle-controlled treatment period:

For both the safety and exploratory efficacy analyses, the baseline will be defined as the last non-missing assessment prior to the first trial treatment dose (including unscheduled assessments). If the last non-missing assessment is performed on the same date as the first trial treatment and time is not available, the assessment will be considered as baseline, except for AEs and medications starting on the first trial treatment dose date which will be considered post-baseline.

- Open-label extension period:

For the safety analyses, the OLE baseline will be defined as the last non-missing assessment prior to the first delgocitinib cream 20 mg/g dose. This definition will be used for summarizing the change from the OLE baseline for the subject who entered OLE period.

For the exploratory efficacy analyses, the baseline will be defined as the last non-missing assessment prior to the first trial treatment dose (including unscheduled assessments) from the vehicle-controlled treatment period for all subjects.

Change from baseline is defined for both the vehicle-controlled treatment period and OLE as the post-baseline value minus the baseline value unless otherwise specified. Percent change from baseline will be calculated as follows: Percent change from baseline = (Change from baseline / Baseline) x 100

For the pruritus NRS, burning sensation NRS, and pain NRS, the baseline scores will be defined as the average of all non-missing daily 24-hour NRS scores reported over the last 7 days prior to randomization (prior to the first application of the IMP).

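### The pooled OLE safety column is indexed by trial visit and so mixes exposure durations 12 weeks apart; add a summary by time since first delgocitinib application that combines both arms' first 12 weeks

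*Combined protocol and SAP*

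**What the plan says.** Section 6.3 states that "approximately 30 subjects will be randomized 1:1 to delgocitinib cream 20 mg/g or vehicle cream". Section 4.1 then puts every completer on active treatment: "All subjects who complete the vehicle-controlled treatment period will then continue into the OLE and apply delgocitinib cream 20 mg/g BID for 12 weeks". Footnote g of Table 1 fixes the changeover: "The first application of the OLE (delgocitinib cream 20 mg/g) is on the morning of Week 12".

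For OLE safety, Section 9.3.4.2 says: "Summaries will be provided for 1) treatment group in the OLE and for 2) randomized treatment groups in vehicle-controlled treatment period". It sets the baseline by arm. The first rule is "Change from baseline will be analyzed using change from vehicle-controlled treatment period baseline for subjects who received delgocitinib during the vehicle-controlled treatment period"; the second is "change from OLE baseline for subjects who received placebo during the vehicle-controlled treatment period" (the comparator is vehicle, so the word placebo there is only loose wording). Section 9.3.2 gives the general definition for safety: "the OLE baseline will be defined as the last non-missing assessment prior to the first delgocitinib cream 20 mg/g dose".

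Section 9.3.4.1, whose general rules carry over to the OLE, tabulates laboratory results and vital signs by treatment group and scheduled visit. It assigns adverse events to a period by whether onset falls before Week 12 or from Week 12 onward. Section 3 lists as an exploratory endpoint the number of TEAEs in the OLE, counted to Week 26. Safety analysis is descriptive throughout.

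Table 1 schedules haematology, biochemistry and vital signs at Weeks 4, 8, 12, 16, 20 and 24. Section 2.2.1 says: "Lymphocytopenia is therefore considered an important potential risk for delgocitinib cream".

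**The concern.** In the OLE there is only one treatment, so a summary by OLE treatment group is a single column holding both randomised arms. In that column, change is anchored to the start of delgocitinib but the time axis is the trial visit. At any OLE visit, one half of the column has had 12 more weeks of delgocitinib than the other half, and the mean describes neither.

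The second part is a missed opportunity. The trial will observe a first 12-week course of delgocitinib in both arms, on matching laboratory and vital-sign schedules. The Protocol Version History gives comparable monitoring of new starters in either period as a reason for the changes to OLE safety monitoring. Yet Section 9.3.4 describes no summary that puts the two first courses together. With about 15 subjects per arm, that leaves each first-exposure estimate resting on about half of the available subjects, in a trial that names lymphocytopenia as an important potential risk.

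**Working it through.** The documents give no figure for the precision of the OLE safety summaries, so there is none to reproduce.

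**Inputs.** About 30 subjects randomised 1:1, so about 15 per arm (Section 6.3). Delgocitinib starts at Day 1 in the delgocitinib arm and at Week 12 in the vehicle arm (Section 4.1; Table 1, footnote g). Laboratory and vital-sign visits are as in Table 1. The documents give no dropout rate, so the share *d* of the vehicle arm that does not enter the OLE is an assumption, shown from 0% to 30%.

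**Step 1: exposure behind the pooled column.** Weeks since first delgocitinib at visit week *w* are *w* in the delgocitinib arm and *w* − 12 in the vehicle arm.

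| Visit | Delgocitinib-first | Vehicle-first | Mean at 15/15 | Mean at 15/12 |
|---|---|---|---|---|
| Week 16 | 16 | 4 | 10.0 | 10.7 |
| Week 20 | 20 | 8 | 14.0 | 14.7 |
| Week 24 | 24 | 12 | 18.0 | 18.7 |

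For example, at Week 16 with 15/15: (15 × 16 + 15 × 4)/30 = 10. The gap is 12 weeks at every visit, and no subject nominally has the mean duration.

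**Step 2: can the data be aligned?** Yes. The delgocitinib arm's Weeks 4, 8 and 12 correspond to the vehicle arm's Weeks 16, 20 and 24, and laboratory tests and vital signs are scheduled at all six. Each arm's planned baseline is its last value before first delgocitinib, which is the baseline the alignment needs.

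**Step 3: number with a first 12-week exposure.** n = 15 + 15 × (1 − *d*), taking all 15 of the delgocitinib arm as contributing.

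- *d* = 0: n = 30
- *d* = 10%: n = 28.5
- *d* = 20%: n = 27
- *d* = 30%: n = 25.5

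Thirty is therefore a ceiling.

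**Step 4: what the larger n gives.** After zero events, the one-sided 95% upper limit solves (1 − *p*)^n = 0.05, so *p* = 1 − 0.05^(1/n). The chance of at least one event at true risk *r* is 1 − (1 − *r*)^n.

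| n | Zero-event upper limit | P(≥1 event), r = 5% | P(≥1 event), r = 10% |
|---|---|---|---|
| 15 | 18.1% | 53.7% | 79.4% |
| 27 | 10.5% | 75.0% | 94.2% |
| 30 | 9.5% | 78.5% | 95.8% |

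For a mean change with the same SD, the standard error at n = 30 is √(15/30) = 0.71 times that at n = 15, about 29% smaller.

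**Step 5: adverse events.** Adding the two planned AE tables by hand does not give a like-for-like first-exposure summary. The vehicle-controlled window is 12 weeks, while the OLE window runs from Week 12 to Week 26, which is 14 weeks. Equal windows have to be specified.

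**The case against.** The strongest reply is that Section 9.3.4.2 already asks for summaries by randomised arm. The vehicle-first column then shows change at 4, 8 and 12 weeks of exposure, unmixed, and the delgocitinib arm's first 12 weeks appear in the vehicle-controlled tables. A reader can set the two side by side. This stands: only the pooled column mixes durations.

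Three stronger readings that a reader might infer do not hold.

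- *The arms have inconsistent baselines.* They do not. Both rules amount to the last value before first delgocitinib, as Section 9.3.2 defines it. A common Day 1 baseline would not remove the mixing, which comes from indexing by visit.
- *An early lymphocyte fall would be blunted.* With equal arms the pooled mean is half the sum of the early change in new users and the later change in established users. It understates the early fall only if established users have partly recovered; if the fall persists, pooling does not hide it. The documents give no time course, and Section 2.2.1 reports low systemic exposure and generally no clinically significant laboratory changes with the cream. Clinically significant laboratory changes are also recorded as AEs and listed by subject.
- *Half of the first-exposure data are left out of any estimate.* They are not. The vehicle arm's OLE events are summarised separately; they are just not combined with the other arm's.

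Two further points stand. The pooled OLE count of TEAEs to Week 26 serves a listed endpoint, so it should not be replaced, and windows ending at Week 24 would lose follow-up events. Also, Section 9.3.1 defers the analysis strategy to a separate SAP that is not part of the text reviewed, so the absence of a combined summary can be stated only of this document.

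**Conclusion.** The point holds as a modest improvement to a descriptive analysis. The pooled OLE column for laboratory and vital-sign change averages exposure durations that differ by 12 weeks at every OLE visit, and the document describes no summary combining the first 12 weeks of delgocitinib from both arms.

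Combining them would take n from about 15 to at most about 30, and the zero-event upper limit from 18.1% to 9.5%. At an assumed 20% non-entry from the vehicle arm the figures are n = 27 and 10.5%. These numbers measure precision gained; they do not show bias in any planned estimate. They assume 15 per arm, nominal visit times and no loss from the delgocitinib arm before 12 weeks.

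No test or error rate is affected, because safety is not tested.

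**What to change.** Keep every summary now planned: the by-arm tables, the randomised vehicle-controlled comparison and the pooled OLE TEAE count to Week 26. Add to Section 9.3.4.2, or to the separate SAP, one descriptive summary of laboratory tests, vital signs and TEAEs by time since first delgocitinib application:

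- **Exposure weeks 0–12:** the delgocitinib arm's Day 1 to Week 12 combined with the vehicle arm's Week 12 to Week 24, over equal windows. Pair Weeks 4, 8 and 12 with Weeks 16, 20 and 24, use the baselines already defined, and show n at each point.
- **Later exposure:** the delgocitinib arm only.
- **Week 24–26 follow-up TEAEs:** reported separately, so that none is lost and the windows stay equal.

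Footnote the limitation: about half of the combined column is open-label and consists of vehicle-arm completers, the combination is not randomised, and the OLE visit windows are ±4 days against ±2 days. The cost is a few sentences and a few tables. No new data, visit or procedure is needed.

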#### **9.3.5 Molecular Signature Changes Analyses**

Molecular signature changes analyses will be evaluated on the basis of the PD analysis set. A MMRM will be used to detect any overall differences in the treatment effect at Week 12 compared to baseline in the molecular measurements. This formulation intrinsically models the within patient correlation structure as in the case of a paired t-test. This approach introduces less bias than restricting the analysis for those patients who completed the trial. Time points (baseline, Week 12), treatment group (active, vehicle, and healthy), and tissue (lesional and non-lesional) will be considered as fixed factors, while participant ID will be included as random factor.

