**Molecular Signature Changes Analyses:**  
A Mixed Effect Model Repeated Measurement (MMRM) will be used to detect any overall differences in the treatment effect at Week 12 compared to baseline in the molecular measurements. This formulation

[figure not shown]
Name of Sponsor/Company:	Name of Investigational Product:	Name of Active Ingredient:
LEO Pharma A/S	Delgocitinib cream 20 mg/g	Delgocitinib
intrinsically models the within patient correlation structure as in the case of a paired t-test. This approach introduces less bias than restricting the analysis for those patients who completed the trial. Time points (baseline, Week 12), treatment group (active, vehicle, and healthy), and tissue (lesional and non-lesional) will be considered as fixed factors, while participant ID will be included as random factor.		
Safety Analyses:  Safety data will be summarized descriptively per cohort. No missing data will be imputed, and no inferential statistics are planned. For Cohort 1, the safety analysis will include reported AEs, including TEAEs, and other safety information (ie. clinical laboratory evaluations and vital signs). For Cohort 2, the safety analysis will include reported procedural complications.		
Efficacy Analyses:  The comparison between the groups for the exploratory efficacy endpoints involving change from baseline will be done using a MMRM, where the absolute change from baseline will be the dependent variable; the treatment group, the visit, and an interaction term for the treatment-by-visit will be the fixed effects; and the baseline value will be the covariate.  The other efficacy endpoints involving proportions of pruritus NRS, burning sensation NRS, and pain NRS will be analyzed using a Chi-square test.		

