#### Cohort 1:

On Day 1, all subjects will have 2 skin biopsies (4-mm) collected prior to the first IMP application (1 from a lesional hair follicle within the target area and 1 from a non lesional hair follicle [eg, on the occipital scalp]). On Week 12, 1 skin biopsy (4-mm) will be collected from a hair follicle within the lesional target area (outside the scar of previous biopsies). Each biopsy will be split in half. One part will be used for IHC and the other part will be used for gene expression analysis.

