## 9.3 Statistical Analyses

### 9.3.1 General Approach

Continuous variables will be summarized in tables and will include the number of subjects, mean, standard deviation (SD), median, minimum, maximum, first (Q1) and third (Q3) quartiles. Categorical variables will be presented in tables as frequencies and percentages.

All details regarding the efficacy and safety variable definitions, analyses strategy, statistical justification, and techniques for handling missing values will be detailed in a separate statistical analysis plan (SAP) that will be prepared before the database is locked and any analyses are undertaken. Any deviation(s) from the SAP will be described and justified in the final report, as appropriate. Statistical analysis related to molecular signature changes/PD analyses (ie, skin biopsies, tape strips, and skin microbiome) will be described in a separate SAP prepared by the specialty laboratory in charge of these analyses.

All statistical tests will be two-sided and will be performed with a significant level of 0.05, unless otherwise specified in the SAP.

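### Read literally, the primary molecular model scales the active-vehicle difference in lesional change by a variance pooled over unlike biopsies, so its standard error may be too small or too large

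*Combined protocol and SAP*

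**What the plan says.** Section 9.3.5 sets the aim: "A MMRM will be used to detect any overall differences in the treatment effect at Week 12 compared to baseline in the molecular measurements". Its model has fixed terms for visit and for study group, with the healthy cohort as a third group beside the two arms. On the remaining terms it says: "tissue (lesional and non-lesional) will be considered as fixed factors, while participant ID will be included as random factor". It justifies the choice as follows: "This formulation intrinsically models the within patient correlation structure as in the case of a paired t-test". The synopsis repeats this.

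Neither place states a residual covariance structure, a variance that differs by tissue or cohort, an interaction term or a degrees-of-freedom method. Section 9.3.1 says that the molecular analyses "will be described in a separate SAP prepared by the specialty laboratory in charge of these analyses". That SAP is not among the documents.

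The samples are set out in Section 8.3.1. On Day 1 each FFA subject gives two biopsies, "1 from a lesional hair follicle within the target area and 1 from a non lesional hair follicle". At Week 12 there is one more, lesional only. Each healthy subject gives two on Day 1, frontal and occipital.

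**The concern.** A single participant random effect with a common residual gives every sample the same variance and every pair of samples from one person the same correlation. With one Day 1 and one Week 12 lesional sample per subject, the residual variance would reflect only the lesional change, and the comparison with a paired t-test would be apt. Here a third FFA sample, from non-lesional occipital scalp, also feeds that residual. How far it differs from the lesional samples says nothing direct about how variable the lesional change is, yet it helps to set the standard error of that change.

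This is the analysis of the primary endpoint. If the pooled variance is too small, a molecular effect is claimed too readily. If it is too large, power is lost. Adding a treatment-by-time term, which the section does not list, would not cure this.

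**Working it through.** **The plan's own power figure.** Section 9.1 gives log2 differences (SD) of 4.851 (4.411), 5.298 (5.512) and 4.559 (4.891). It assumes a 90% against a 5% reduction, 15 per arm and a one-sided 5% two-sample t-test. Taking the effect as 0.85 times the log2 difference:

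- CXCL9: effect 0.85 × 4.851 = 4.123; SE 4.411 × √(2/15) = 1.611; noncentrality 2.56; power 0.803 on 28 df.
- CXCL10 and IFN-γ, by the same method: 0.705 and 0.682.
- At least one gene, uncorrelated tests: 1 − (0.197 × 0.295 × 0.318) = 0.98. The claim of at least 80% is reproduced as a lower bound.

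**The literal model.** To make the contrast estimable, each group-by-sample cell is given its own mean. With complete data the estimate is then the difference between arms in mean lesional change. A REML fit agreed to rounding error. Only the standard error is in question.

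- Residual df: FFA (30 − 2) × (3 − 1) = 56; healthy (5 − 1) × (2 − 1) = 4; total 60.
- Model SE = √(4s²/15), where s² is the pooled within-subject variance.
- True SE = √(2V/15), where V is the variance of the lesional change.
- The two agree when s² = V/2.

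**Size of the mismatch.** Let σ be the lesional SD (the same at both times and in both arms), k the non-lesional/lesional SD ratio, ρ the correlation of the two lesional samples, and r the lesional/non-lesional correlation. For the FFA samples, s² is half the average of the three pairwise difference variances:

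- lesional change: 2σ²(1 − ρ);
- lesional against non-lesional, twice: σ²(1 + k² − 2rk).

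Dividing s² by V/2 = σ²(1 − ρ) gives

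variance ratio = [2 + k² − ρ − 2rk] / [3(1 − ρ)].

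The documents give none of k, ρ or r, so the values below are assumed. The ratio columns use FFA samples only. Errors come from simulation (15 per arm, 5 healthy × 2 samples, 60 df), with healthy skin as variable as non-lesional skin.

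| k | ρ | r | Variance ratio | SE ratio | Two-sided error at nominal 5% |
|---|---|---|---|---|---|
| 0.25 | 0 | 0 | 2.0625/3 = 0.69 | 0.83 | about 11% |
| 0.5 | 0.3 | 0.3 | 1.65/2.1 = 0.79 | 0.89 | about 9% |
| 0.5 | 0.5 | 0.5 | 1.25/1.5 = 0.83 | 0.91 | about 8% |
| 1 | 0.5 | 0.3 | 1.9/1.5 = 1.27 | 1.13 | about 3% |
| 1 | 0.5 | 0 | 2.5/1.5 = 1.67 | 1.29 | about 1% |
| 0.75 | 0.5 | 0.375 | 1.5/1.5 = 1.00 | 1.00 | about 5% |
| 0.5 | 0.2 | 0.5 | 1.55/2.4 = 0.65 | 0.80 | about 12% |
| 0.5 | 0 | 0.5 | 1.75/3 = 0.58 | 0.76 | about 14% |

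Using the variance of the lesional change itself (28 df), the error stayed at about 5% in every scenario.

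**Healthy subjects.** They supply 4 of 60 residual df (6.7%) and move the SE by about 0 to 3%. With healthy SD equal to lesional SD, the first three rows fall to roughly 10%, 8% and 7%. The non-lesional sample is the main driver.

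**Power in the most conservative row (k = 1, ρ = 0.5, r = 0).** Here V = σ², which matches the SD used in Section 9.1. Single-gene power is about 65%, 53% and 50%, against 80%, 70% and 68%. For at least one gene: 1 − (0.35 × 0.47 × 0.50) = 0.92.

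**The case against.** Four points on the other side have weight.

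- **The common residual variance is inferred.** The model is labelled an MMRM, which can mean an unstructured covariance, and detail is deferred to the laboratory SAP. This stands as a limit on certainty. But Section 9.3.5 does say how correlation is handled, through participant as the only random factor, and defends that by the paired t-test comparison. A laboratory SAP that follows it inherits the problem, and one that uses another structure leaves the protocol text to be reconciled.
- **A reader might infer that the standard error is wrong unless all variances and correlations are equal.** That is too strong. Equal variances of the paired differences (sphericity) are enough, and even a matching average will do. The sixth row of the table has unequal variances and correlations and a ratio of exactly 1.
- **A reader might infer that the power claim fails.** It does not. Section 9.1 claims power for at least one gene, and that stays at about 92% in the most conservative of the five main scenarios (first five rows).
- **The trial is a single-site, exploratory Phase 2a study.** This lowers the urgency. It does not remove the point, because the plan bases a powered significance claim on these genes.

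**Conclusion.** The point holds in a conditional form. If Section 9.3.5 is carried out as written, the standard error of the primary active-vehicle contrast rests on a pooled variance that need not match the lesional change, and it can be materially off in either direction. In the five main scenarios (k 0.25 to 1, ρ and r 0 to 0.5) two-sided error runs from about 1% to 11%. Less favourable combinations in those ranges reach 12% to 14%, and others sit near 5%.

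These figures rest on assumed variances and correlations, complete data and an added treatment-by-sample term. The documents fix neither the direction nor the size, so they do not support a statement that the test is liberal, or that it is conservative. Nor do they support treating healthy skin as a main cause. The plan should be changed because a structure that avoids the risk costs almost nothing; the sample size claim is unaffected.

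**What to change.** In Section 9.3.5, the synopsis and the laboratory SAP:

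- Keep all samples, but specify an unstructured 3x3 within-subject covariance for lesional Day 1, non-lesional Day 1 and lesional Week 12.
- Give healthy subjects a separate covariance.
- Name a small-sample degrees-of-freedom method, for example Kenward-Roger.
- State that the active-vehicle contrast in lesional change is estimated from this model, with the terms needed to estimate it.
- Limit the paired t-test sentence to that contrast.

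An ANCOVA of Week 12 on Day 1 lesional expression can serve as a sensitivity analysis. It uses only subjects with a Week 12 biopsy, the kind of restriction that Section 9.3.5 sets out to avoid, and it leaves out the non-lesional and healthy samples. It should therefore not replace the main model.

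The cost is wording and some precision. About 27 to 28 df replace 60, so the critical t is about 2.05 instead of 2.00 and, for the same SE, intervals are about 2.5% wider (2.05/2.00 = 1.025).
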